2.4.5.5.5 Analysis

Immunogenicity will be assessed through summary tables, figures, and listing of individual results by subject. All immunogenicity data related to assessments on the Q6M FU visits will be analyzed using the ITO population on the following analysis groups:

- Caplacizumab total: Subjects who received caplacizumab during the ALX0681-C301 study (during the double blind or the open-label periods).
- Not treated: Subjects who never received Caplacizumab during the ALX0681-C301 trial

All immunogenicity data related to assessments during the recurrence periods will be analyzed using the recurrence population with the following analysis groups:

- Treated with IMP: patients treated with caplacizumab in the ALX0681-C302 study for the specific recurrence episode
- Not Treated with IMP: patients not treated with caplacizumab in the ALX0681-C302 study for a specific recurrence episode

ADA assay results

The number and percentage of subjects per ADA subject category will be summarized.

Incidence of positive ADA samples by visit.

Spaghetti plot of ADA log₁₀ (titer) vs. time. Negative values for ADA (reported as log₁₀ (titer) < 1.98) will be visualized on the graphs as 1.80 (arbitrarily chosen) to allow plotting. The MRD (or sensitivity of the assay) will be visualized as horizontal line at log₁₀ (titer) = 1.98.

mADA assay results

The number and percentage of subjects per mADA subject category will be summarized. This tabulation and analysis will be performed on a subset of the population, consisting of subjects who were classified as ADA positive based on ADA data.

- Each mADA subject category
- Classified as TE ADA within the pre-Ab negative and within the pre-Ab positive population
- Classified as pre-Ab negative, pre-Ab positive, drug-induced TE negative and drug-induced TE positive

Incidence of positive mADA samples by visit.

Spaghetti plot of mADA log₁₀ (titer) vs. time. Negative values for mADA (reported as log₁₀ (titer) < 1.98) will be visualized on the graphs as 1.80 (arbitrarily chosen) to allow plotting. The MRD (or sensitivity of the assay) will be visualized as horizontal line at log₁₀ (titer) = 1.98.

ADA/mADA assay results (overall subject classification)

The number and percentage of subjects will be summarized by group using following categorization.

- Each overall subject category
- Classified as TE ADA within the pre-Ab negative and within the pre-Ab positive population
- The number and percentage of subjects classified as pre-Ab negative, pre-Ab positive, drug-induced TE negative and drug-induced TE positive

NAb assay result

The number and percentage of subjects will be summarized using following categorization. This analysis will be performed on subset of the population, consisting of subjects who were classified as ADA positive based on ADA data.

- Each NAb subject category
- Classified as pre-dose negative, pre-dose positive, TE negative and TE positive

Alternative NAb (null variant) assay result

The number and percentage of subjects will be summarized using following categorization.

- Each alternative NAb subject category
- Classified as pre-dose negative, pre-dose positive, TE negative and TE positive

Incidence of positive alternative NAb samples by visit.

Spaghetti plot of alternative NAb log₁₀ (titer) vs. time. Negative values for alternative NAb (reported as log₁₀ (titer) < 1.98) will be visualized on the graphs as 1.80 (arbitrarily chosen) to allow plotting. The MRD (or sensitivity of the assay) will be visualized as horizontal line at log₁₀ (titer) = 1.98.

Individual line plots of ADA log₁₀ (titer), mADA log₁₀ (titer), NAb log₁₀ (titer), alternative NAb log₁₀ (titer), PK, RICO activity, vWF:Ag concentration, over time with indication of PE treatment days and treatment with rituximab. PE and rituximab treatment days should be visualized on the plot. For ADA, mADA, and alternative NAb titer plotting, negative values (reported as log₁₀ (titer) < 1.98) will be visualized on the graphs as 1.80 (arbitrarily chosen) to allow plotting. The MRD (or sensitivity of the assay) will be visualized as horizontal line at log₁₀ (titer) = 1.98. Negative values for NAb assay (reported as log₁₀ (titer) < 0.36) will be visualized on the graphs as 0.20. The MRD of the NAb assay will be visualized as a horizontal line at log₁₀ (titer) = 0.36. Different responses can be plotted against separate Y-axes above each other, but scale of time-axis should be identical for each plotted response.

Listing of all immunogenicity parameters (ADA log₁₀ (titer), mADA log₁₀(titer), NAb result log₁₀(titer), alternative NAb result log₁₀(titer)) at each time point.

Listing of subject classification based on ADA assay, mADA assay, overall subject classification (based on ADA and mADA assay results) and listing of subject classification based on NAb assay and alternative NAb assay.

Scatter plot of drug concentration (logarithmic) by subject category based on the ADA, mADA, NECA and Nab results. Connect means per group to visualize mean drug concentrations per subject category.

Scatter plot of % change from baseline vWF:Ag concentrations (logarithmic) by subject category based on the ADA, mADA, NECA and Nab results. Connect means per group to visualize mean % change from baseline vWF:Ag concentrations per subject category.

Scatter plot of RICO activity (logarithmic) by subject category based on the ADA, mADA, NECA and Nab results. Connect means per group to visualize mean RICO activity per subject category.

Km plot time to platelet count response by subject category based on the ADA, mADA, NECA and Nab results.

Subgroup analysis by hypersensitivity analysis (no or at least one hypersensitivity reaction) based on ADA/mADA results (overall subject classification) and based on NAb results

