1.2.3. NONCLINICAL STUDIES

All relevant nonclinical studies conducted with caplacizumab are described in the Investigator's Brochure.

- Pharmacology: The pharmacodynamic (PD) properties of caplacizumab were studied in *in vitro* and *in vivo* studies.
Caplacizumab was shown to:
 - Bind to the A1 domain of vWF in normal and ultra large multimers.
 - Inhibit concentration-dependently and completely the interaction of (UL)vWF with platelets.
 - Inhibit *in vitro* and *in vivo* arterial thrombus formation.

- Prevent *in vitro* platelet string formation with ULvWF.
 - Inhibit completely ristocetin-induced platelet aggregation (RIPA) and ristocetin cofactor activity (RICO) *in vitro* and *in vivo*.
 - Decrease dose-dependently and saturably FVIII activity and von Willebrand factor antigen (vWF:Ag) levels with recovery after treatment stop.
 - Not increase surgical bleeding *in vivo*.
 - Prevent and treat thrombocytopenia and schistocytic hemolytic anemia in a baboon model of acquired TTP.
- Pharmacokinetics: The pharmacokinetic (PK) properties of caplacizumab were analyzed in 4 cross-reactive species (baboon, farm pig, cynomolgus monkey and guinea pig). Different routes of administration were assessed, namely intravenous (i.v.), subcutaneous (s.c.) and intramuscular (i.m.). The terminal half-life ($t_{1/2}$) of caplacizumab - more precisely caplacizumab bound to vWF - ranges between 5-36 hours across the species. The complex of caplacizumab and vWF is eliminated hepatically, possibly via a target-specific pathway and the excess of unbound drug is rapidly cleared via renal filtration. Consequently, after i.v., s.c. or i.m. administration, non-linear kinetics were observed: exposure does not increase proportionally to the dose. This PK behavior limits the potential for overdosing. The absolute bioavailability of caplacizumab after s.c. administration, in cynomolgus monkey, ranged from 82% to 97%.
 - Toxicology: Toxicity studies include:
 - Single dose toxicity studies in cynomolgus monkey and guinea pig after i.v. and s.c. administration,
 - 2-week repeated dose toxicity studies in cynomolgus monkey after i.v. and s.c. administration,
 - 13-week repeated dose toxicity studies in cynomolgus monkey and guinea pig after s.c. administration and
 - A 26-week chronic dose toxicity study in cynomolgus monkey after s.c. administration.

The toxicology data revealed:

- Neutralization of vWF activity throughout dosing period (as measured through RICO).

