patients in the caplacizuamb treatment group and 18 (9.8%) patients in the abciximab treatment group and were most frequently 'injury, poisoning and procedural complications' and 'cardiac disorders'. By Day 30 there was 1 death in the abciximab group and none in the caplacizumab group. After 1 year of FU, there were 5 deaths in each treatment arm. All but one of the deaths were considered to be unlikely/not related to the study drug. This other death (in the caplacizumab treatment group) was considered possibly related to treatment.

In this Phase II study, treatment-emergent antibodies were detected in 10.9% of the caplacizumab-treated subjects. No neutralizing antibodies were detected.

The PD assessments showed an immediate drop in RICO activity 5 to 10 minutes after the caplacizumab bolus injection. Clinically relevant RICO inhibition (< 20%) was maintained for 24 hours post-bolus in the caplacizumab group which was accompanied by an expected transient and mild decrease in vWF antigen and FVIII activity.

Phase III study

One Phase III study is currently ongoing in the development of caplacizumab for the treatment of acquired TTP:

Study ALX0681-C301 (HERCULES) is a randomized, double blind, placebo-controlled study to evaluate the efficacy and safety of caplacizumab treatment in addition to standard of care treatment (daily PE + corticosteroid treatment) in subjects with an acute episode of acquired TTP. The study will evaluate the efficacy of caplacizumab in more rapidly restoring normal platelet counts and the effect of treatment with caplacizumab on a composite endpoint of TTP-related mortality, prevention of recurrence of the presenting TTP episode and prevention of major thromboembolic events during study drug treatment.

After confirmation of study eligibility and after the start of PE treatment, approximately 92 subjects with a clinical diagnosis of acquired TTP are to be randomized in a ratio of 1:1 to either receive caplacizumab or placebo in addition to standard of care therapy. Subjects are treated for 30 days after stop of daily PE treatment (with a possibility of weekly extensions for a maximum of 4 weeks in case of persistent signs and symptoms of continued underlying disease activity) with a 4 week FU period. Subjects who experience a first exacerbation or a first relapse during treatment extension are to crossover to open-label caplacizumab.

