2 STATISTICAL AND ANALYTICAL PROCEDURES

2.1 ANALYSIS ENDPOINTS

2.1.1 Demographic and baseline characteristics

For analysis related to the on-study period, the baseline is defined as the screening/baseline visit.

For analysis related to the recurrence period, the baseline value is defined as the recurrence visit of that recurrence episode.

All baseline parameters are presented along with the on-treatment summary statistics in the sections ([Section 2.4.5](#) and [Section 2.4.4](#)).

Demographic characteristics

Demographic variables are:

- Gender at birth: (Male, Female),
- Race: (not allowed to ask / white / black or African American / Asian / American Indian or Alaska native / native Hawaiian or other Pacific islander / other),
- Age in years at inform consent
- Ethnicity (Hispanic, non-Hispanic),

Medical or surgical history

Medical history includes:

- General medical history
- TTP-related medical history: TTP episodes and major thromboembolic events (e.g., myocardial infarction, cerebrovascular accident, pulmonary embolism, deep venous thrombosis, transient ischemic attack, heart failure, unstable angina, coronary revascularization)
- History of hypersensitivity to IMP in study ALX0681-C301

This information will be coded using version 22.0 of Medical Dictionary for Regulatory Activities (MedDRA).

Vital signs

Vital signs at baseline are weight in kilograms, height, blood pressure and pulse (assessed after 5 min in supine position).

Baseline disease characteristics

Baseline disease characteristics are measured at the recurrence visit. It includes:

- ADAMTS13 activity at admission or baseline: <10% / ≥10%
- Baseline organ damage markers: (LDH, TnI and serum creatinine): ≤ULN / >ULN
- Baseline platelet count.
- Baseline RICO activity, vWF:Ag concentration

Any technical details related to computation, dates, and imputation for missing dates are described in [Section 2.5](#).

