2.4 STATISTICAL METHODS

For continuous parameters, descriptive statistics will be presented when $n \geq 2$. When $n = 1$, only sample size (n) and mean, i.e. the value itself, are shown. Descriptive statistics will include the number of non-missing data points (n), the arithmetic mean, the standard deviation (SD) (for baseline summaries) or standard error (SE) (for post-baseline, change from baseline, or percentage change summaries), the median, minimum and maximum.

For categorical parameters, frequency tabulations are prepared, consisting of frequency counts (non-missing observations) and percentages. Missing values will not be included in the denominator count when computing percentages.

Descriptive statistics of PK concentrations and PD data will additionally include 5% and 95% percentiles, SD of arithmetic mean, coefficient of variation (CV)% of arithmetic mean, geometric mean and geometric SD.

For the graphs showing mean values or percentages, an SE flag will be shown. For PK graphs showing geometric mean values, a geometric SD flag will be shown.

- Change from baseline and percentage change from baseline
- The change from baseline will be calculated for all post-baseline time points as:
- Change from baseline at time point $t = \text{value at time point } t - \text{baseline value}$.
- Percentage change from baseline at time point $t = 100 * \frac{[\text{value at time point } t - \text{baseline value}]}{\text{baseline value}}$.
- Change from baseline and percentage change from baseline will be calculated separately for each of the analysis periods from their respective baseline values.

Relative number of days

The relative day (DY) is calculated as follows:

- Visit date – reference date + 1 day, when the visit date is on or after the reference date
- Visit date – reference date, when the visit date is before the reference date.

The reference date is the date of first intake of the study drug, which by definition has DY=1. There is no DY=0.

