Study Visit	Recurrence Visit	Day 3 visit Treatment Day 3	Week 1 visit Post-daily PE Day 1 (1 day after last daily PE)		
Review of caplacizumab treatment criteria	X				
Pregnancy test ^a	X				
TTP recurrence information ^b	X		X		X
Study drug administration				>	
PE information			X		
Concomitant medication					>
Adverse events					>
Supine heart rate & blood pressure ^c	X	X	X	X ^d	X
Physical examination	X	X	X	X ^d	X
SF-36					X
Clinical laboratory analyses + urinalysis ^e	X	X	X	X	X
Organ damage markers: TnI ^f	X	X	X	X	X
ADAMTS13 activity ^f	X	X	X	X	X
Immunogenicity (ADA panel) ^{f,g}	X	X	X	X	X
PK ^f	X	X	X	X	X
PD parameters ^{f,h}	X	X	X	X	X

^a Pregnancy test (urine or blood) for female subjects of childbearing potential will be assessed per local laboratory.

^b TTP recurrence information includes presenting symptoms (assessed at recurrence visit), duration (assessed at the Week 1 visit) and outcome (assessed at the recurrence FU visit).

^c Heart rate and blood pressure to be assessed after 5 min in supine position.

^d To be assessed at the post-daily PE Day 29 only.

^e Clinical laboratory analyses include hematology (Hb, Hct, RBC, WBC, platelets); chemistry (AST, ALT, LDH, creatinine, protein, cholesterol and CRP). Urinalysis includes assessment of albumin. The results of assessment of platelet count and LDH levels performed as per standard of care (by a local laboratory) at any time during the recurrence period will be collected in the eCRF, if available.

- f* At the recurrence visit and the Treatment Day 3 visit, samples need to be collected prior to start of the PE treatment and/or study drug administration (whatever comes first). At all subsequent visits, blood samples need to be taken prior to study drug administration.
- g* In case of a severe and/or serious hypersensitivity reaction, an additional blood sample to characterize the reaction should be collected as soon as possible after the start of the event.
- h* PD parameters include RICO and vWF:Ag.

Table 6 Schedule of Assessments in Case of TTP Recurrence (in Case Treatment with Caplacizumab is not Initiated)

Study Period	Recurrence Period (no caplacizumab)	
	Recurrence Visit Recurrence Day 1	Recurrence FU visit 30 days after end of daily PE
TTP recurrence information ^a	X	X
PE information		X
Concomitant medication		→
Adverse events		→
Supine heart rate & blood pressure ^b	X	X
Physical examination	X	X
SF-36		X
Clinical laboratory analyses + urinalysis ^c	X	X
Organ damage markers: TnI ^d	X	X

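### The vWF:Ag figure by antibody category puts a signed percent change on a logarithmic scale, so observations at or below baseline and negative group means cannot be drawn

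*SAP*

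**What the plan says.** The immunogenicity analysis (SAP 2.4.5.5.5) lists a "Scatter plot of % change from baseline vWF:Ag concentrations (logarithmic) by subject category based on the ADA, mADA, NECA and Nab results" and then instructs: "Connect means per group to visualize mean % change from baseline vWF:Ag concentrations per subject category". The scatter plots on either side of it, for drug concentration and RICO activity, carry the same logarithmic tag.

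SAP 2.4 defines percent change as 100 times the difference between value and baseline, divided by baseline, and adds that "Change from baseline and percentage change from baseline will be calculated separately for each of the analysis periods from their respective baseline values". For recurrences, SAP 2.1.1 fixes the reference: "For analysis related to the recurrence period, the baseline value is defined as the recurrence visit of that recurrence episode". The footnotes to Table 5 in SAP Appendix A place that sample before treatment: at the recurrence visit and on treatment Day 3, "samples need to be collected prior to start of the PE treatment and/or study drug administration (whatever comes first").

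On direction, Protocol 1.2.3 reports that caplacizumab was shown to "Decrease dose-dependently and saturably FVIII activity and von Willebrand factor antigen (vWF:Ag) levels with recovery after treatment stop". Protocol 1.2.4 says that RICO inhibition in the Phase II study in percutaneous coronary intervention was "accompanied by an expected transient and mild decrease in vWF antigen and FVIII activity". Protocol 1.2.5 counts vWF decreases that need no supplementation among the expected, very common adverse events.

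**The concern.** The figure pairs a quantity that can be negative with a scale that accepts only positive numbers, and negative is the direction in which the drug is expected to move it.

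Protocol 3.6.5 commits to relating immunogenicity to PK and PD by subject category. SAP 2.4.5.5.4 says the relevance of potentially neutralising antibodies should be judged against PK, PD, safety and efficacy. For vWF:Ag, this figure is where the SAP does so. If antibodies blunt the effect, the sign would be a smaller fall in antibody-positive categories. A figure that can draw only rises cannot show one fall as smaller than another.

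**Working it through.** The plan states no number to reproduce, so the check applies its own formula and then illustrates the size under stated assumptions.

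**Step 1: the SAP formula on a log scale.** Percent change = 100 × (value − baseline)/baseline, with baseline set to 100. Percent of baseline = 100 × value/baseline.

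| Value | Percent change | log10 of percent change | log10 of percent of baseline |
|---|---|---|---|
| 50 | −50 | undefined | 1.699 |
| 70 | −30 | undefined | 1.845 |
| 80 | −20 | undefined | 1.903 |
| 90 | −10 | undefined | 1.954 |
| 100 | 0 | undefined | 2.000 |
| 110 | +10 | 1.000 | 2.041 |
| 150 | +50 | 1.699 | 2.176 |

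Only rises can be drawn as percent change. All seven values can be drawn as percent of baseline. A connected group mean fails in the same way whenever it is zero or negative.

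**Step 2: is there a rescue rule?** SAP 2.4.5.5.5 sets plotting substitutes for negative antibody results (1.80 for ADA, mADA and alternative NAb titers; 0.20 for NAb). SAP 2.5.1 covers values beyond a detection limit. Neither covers a zero or negative percent change.

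**Step 3: how many points could be lost?** The documents give neither a mean nor a spread for the vWF:Ag change, so both are assumptions here. Let value/baseline be lognormal with geometric mean ratio g and coefficient of variation CV, and let s = √ln(1 + CV²).

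- Share not drawable: Φ(−ln g / s).
- True mean percent change: 100 × (g√(1 + CV²) − 1).

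Example with g = 0.8 and CV = 30%: s = √ln 1.09 = 0.294; −ln 0.8 / 0.294 = 0.223/0.294 = 0.760; Φ(0.760) = 0.776. About 78% of points are lost. The true mean is 100 × (0.8 × 1.044 − 1) = −16.5%.

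| g | Lost, CV 20% | Lost, CV 30% | Lost, CV 50% |
|---|---|---|---|
| 1.0 | 50.0% | 50.0% | 50.0% |
| 0.9 | 70.3% | 64.0% | 58.8% |
| 0.8 | 87.0% | 77.6% | 68.2% |
| 0.7 | 96.4% | 88.8% | 77.5% |
| 0.6 | 99.5% | 95.9% | 86.0% |

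For g from 0.6 to 0.9, the true mean runs from about −39% to about +1%. The mean of the drawable points alone runs from about +7% to +46%, because it is positive by construction. With no shift at all (g = 1.0), half the points are still lost.

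**The case against.** The strongest reply is that this is a drafting slip with little consequence. The tag appears on three neighbouring scatter plots and suits the other two, so it may have been carried over. A plot missing most of its points would be noticed in programming. No formal test is planned (SAP 2.4.4.8). Drug concentration, RICO and time to platelet response are also shown by antibody category, and raw vWF:Ag appears in individual line plots, summaries and listings (SAP 2.4.5.5.5 and 2.4.6.2).

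Most of this stands as a limit on impact. It does not repair the specification. The individual line plots and the vWF:Ag summaries are not split by antibody category, so they do not replace this figure. Reading the tag as percent change of log concentration does not help: a fall stays negative whenever the log baseline is positive. If the programmer has to improvise, the handling is not pre-specified.

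Three stronger readings are tempting, and the documents do not support them.

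- A reader might infer that whole subjects disappear, leaving only those without the drug effect. vWF:Ag is sampled repeatedly, so the loss is per observation: a subject with a fall at one visit and a rise at another still appears at the second.
- A reader might infer that the reported group means will come out positive, or that categories will look alike. That requires means recomputed on the drawable points. The SAP asks for mean percent change with no such restriction, so a negative mean would simply be undrawable.
- A reader might infer that most data are lost throughout. The expected fall applies to treatment, with recovery afterwards. Six-monthly visits are largely off drug, and some recurrence episodes are untreated. The two statements quoted on direction come from nonclinical work and from coronary patients, not from TTP patients on daily plasma exchange.

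**Conclusion.** The figure is wrong as specified. Non-positive percent changes and non-positive group means cannot be drawn on a logarithmic scale; this follows from the SAP's own definition and needs no assumption. That losses are heaviest at on-treatment recurrence visits rests on the protocol's expectation that vWF:Ag falls on caplacizumab.

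The size is illustrative only: about 59% to 99.5% of points under a lognormal ratio to baseline with geometric mean 0.6 to 0.9 and CV 20% to 50%.

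The reach is one descriptive figure. Although immunogenicity of repeated treatment is a main endpoint, a reader should not infer that its assessment fails. Subject classifications, incidence by visit, titers and the other displays by antibody category do not use this quantity. What would be lost is the one vWF:Ag comparison by antibody category that the SAP specifies.

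**What to change.** Amend the figure specification in SAP 2.4.5.5.5 in one of two ways:

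- plot value/baseline (percent of baseline) on the logarithmic axis, with geometric means per category; or
- keep percent change on a linear axis, with arithmetic means per category.

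In either case, state that all observations are kept and that the connected means use all of them. The first option keeps the log scale of the neighbouring plots; the second keeps the quantity already named. The cost is one line of the specification and the matching programming change. No new data are needed and no other analysis changes.
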